6.4.1. Treatment of Infusion Reactions

In case of hypersensitivity reactions, the investigator should institute treatment measures deemed medically appropriate in accordance with current medical practice and treatment guidelines. The following treatment recommendations are based on prior experience with Taxol® (containing Cremophor® EL)¹; these and/or other measures deemed medically necessary should be implemented based on the judgment of the investigator. To reduce the risk of infusion reactions caused by Cremophor EL, refer to refer to Section 6.6.1.

Note that the “Grades” listed below do not correspond to NCI CTCAE v5.0 criteria (which are based on response to intervention, and thus are not used here to recommend specific interventions). For the purpose of AE reporting and for determining the need for dose modifications, NCI CTCAE v5.0 grading for allergic reaction should be used.

- Grade 1 allergic reaction/hypersensitivity (e.g., transient flushing, rash, drug fever < 38°C):
 - Supervise at the bedside.
 - Report to Sponsor as an adverse event of special interest (AESI)
- Grade 2 allergic reaction/hypersensitivity (e.g., urticaria, drug fever ≥ 38°C, rash, flushing, dyspnea):
 - Interrupt the infusion and disconnect infusion tubing from subject,
 - Administer IV antihistamines (diphenhydramine 25 to 50 mg and famotidine 20 to 40 mg or class equivalents),
 - After recovery from symptoms, resume the infusion at a half of the infusion rate and if no further symptoms appear, complete the administration of the dose. A target infusion time of up to 3 hours may be appropriate in some cases.
 - Report to Sponsor as an AESI
- Grade 3 or 4 allergic reaction/hypersensitivity (e.g., symptomatic bronchospasm requiring parenteral medication(s) with or without urticaria; allergy-related edema/angioedema; anaphylaxis; hypotension):
 - Stop the infusion with AL101 and disconnect infusion tubing from subject,
 - Administer epinephrine, antihistamines, and nebulized bronchodilators as medically indicated,
 - Consider IV steroids which may prevent recurrent or ongoing reactions,
 - **Report to Sponsor as a serious adverse event (Section 8.3.4),**

¹ Taxol (paclitaxel) label: https://www.accessdata.fda.gov/drugsatfda_docs/label/2011/020262s049lbl.pdf

- Report to Sponsor as an AESI
- Discontinue the subject from IP for a Grade 4 or for a second episode of a Grade 3 reaction.

Other symptoms associated with hypersensitivity reactions include facial flushing, chest pain and tightness, back pain and GI symptoms, leg pain and cough.

Retreatment after a Grade 3 or greater hypersensitivity reaction despite premedication should be discussed between the Sponsor's Medical Monitor and investigator prior to retreatment. If treatment interruption is longer than 28 days, the subject will be discontinued from IP.

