
Dose Modification Criteria for AL101 -Related Adverse Events	AL101 modification at next dose	
	Dose 6 mg QW	Dose 4 mg QW
	
Dose modifications for AL01:
 
Interrupt AL101 until resolution to \leq Grade 1 (refer to Section 6.4.2 and above for management guidelines for diarrhea).
 
Change dose regimen to 6 mg 2 weeks on / 1 week off for first episode
 
Decrease AL101 dose to 4 mg QW for second episode and to 2.4 mg QW for third episode.
 
If the diarrhea does not resolve to Grade 1 by 14 days, the subject will be discontinued from IP (refer to Section 7.2 for handing IP discontinuation).
 
If treatment interruption is longer than 28 days, the subject will be discontinued from IP (refer to Section 7.2 for handing IP discontinuation).
	
Dose modifications for AL01:
 
Interrupt AL101 until resolution to \leq Grade 1 (refer to Section 6.4.2 and above for management guidelines for diarrhea).
 
Decrease AL101 dose to 2.4 mg QW.
 
If the diarrhea does not resolve to Grade 1 by 14 days, the subject will be discontinued from IP (refer to Section 7.2 for handing IP discontinuation).
 
If treatment interruption is longer than 28 days, the subject will be discontinued from IP (refer to Section 7.2 for handing IP discontinuation).

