AST or ALT > 5 times the institutional ULN	Interrupt AL101 until resolution to \leq Grade 1 and then decrease dose to 4 mg QW for first episode and to 2.4 mg QW for second episode.	Interrupt AL101 until resolution to \leq Grade 1 and then decrease dose to 2.4 mg QW.

Dose Modification Criteria for AL101 -Related Adverse Events	AL101 modification at next dose	
	Dose 6 mg QW	Dose 4 mg QW
	
Refer to Section 6.4.3 for hepatic function abnormalities and Figure 2 for drug-induced liver toxicity management.
 
If treatment interruption is longer than 28 days, the subject will be discontinued from IP (refer to Section 7.2 for handing IP discontinuation)..
	
Refer to Section 6.4.3 for hepatic function abnormalities and Figure 2 for drug-induced liver toxicity management.
 
If treatment interruption is longer than 28 days, the subject will be discontinued from IP (refer to Section 7.2 for handing IP discontinuation)..

Hy's law cases (e.g. drug induced liver injury; DILI) as defined in Section 6.4.3.1 and assessed by the investigator and Sponsor	Immediately discontinue IP (refer to Section 7.2 for handing IP discontinuation)	Immediately discontinue IP (refer to Section 7.2 for handing IP discontinuation)
Triglyceride Grade 3 elevations that persist after 4 weeks of medical management	
Interrupt AL101 until resolution to \leq Grade 1 and then decrease dose to 4 mg QW for first episode and to 2.4 mg QW for second episode.
 
If treatment interruption is longer than 28 days, the subject will be discontinued from IP (refer to Section 7.2 for handing IP discontinuation)..
	
Interrupt AL101 until resolution to \leq Grade 1 and then decrease dose to 2.4 mg QW.
 
If treatment interruption is longer than 28 days, the subject will be discontinued from IP (refer to Section 7.2 for handing IP discontinuation).

Infusion-related reaction	For dose modification and management of infusion-related reactions, refer to Section 6.4.1.	For dose modification and management of infusion-related reactions, refer to Section 6.4.1.

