Any other AL101-related Grade 3 nonhematologic adverse event except electrolyte abnormalities that may be managed with supplements	
Interrupt AL101 until resolution to \leq Grade 1 and then change dose regimen to 6 mg 2 weeks on / 1 week off for the first episode.
 
Decrease AL101 dose to 4 mg QW for second episode and to 2.4 mg QW for third episode.
 
If treatment interruption is longer than 28 days, the subject will be discontinued from IP (refer to Section 7.2 for handing IP discontinuation)..
	
Interrupt AL101 until resolution to \leq Grade 1 and then decrease dose to 2.4 mg QW.
 
If treatment interruption is longer than 28 days, the subject will be discontinued from IP (refer to Section 7.2 for handing IP discontinuation).

Grade 4 non-hematologic AEs including Grade 4 non-	Permanently discontinue from IP (refer to Section 7.2 for handing IP discontinuation).	Permanently discontinue from IP (refer to Section 7.2 for handing IP discontinuation).

Dose Modification Criteria for AL101 -Related Adverse Events	AL101 modification at next dose	
	Dose 6 mg QW	Dose 4 mg QW
hematologic lab abnormalities lasting \geq 72 hours		

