If the diarrhea does not resolve to Grade 1 by 14 days, the subject will be discontinued from IP. If treatment interruption is longer than 28 days, the subject will be discontinued from IP (refer to Section [7.2](#) for handing IP discontinuation).

For Grade 4 diarrhea, the subject must be discontinued from IP (refer to Section [7.2](#) for handing IP discontinuation).

3. Interrupt AL 101 dosing

For Grade 2 or 3 diarrhea that is not controlled (i.e., to Grade 1) with loperamide, dosing of AL101 should be interrupted, as continued dosing is likely to result in increased severity of diarrhea. In addition, evaluation of infectious causes should be considered. Based on the mechanism of action and preliminary clinical experience, full gastrointestinal (GI) tract recovery will likely take longer than the time for diarrhea to resolve. Thus, interruption for 5 days to 7 days beyond the resolution of diarrhea should be considered. Depending on the severity, time to onset, and time to resolution of diarrhea, reduction of AL101 dose and/or frequency, omission of future doses, or corticosteroid co-administration should be considered (as outlined in Section 6.6.2). If the diarrhea does not resolve to Grade 1 by 14 days, the subject will be temporarily discontinued from IP. If IP interruption is longer than 28 days, the subject will be permanently discontinued from IP (refer to Section 7.2 for handling IP discontinuation).

4. Increase fluid intake and, if applicable, consider stopping antihypertensive therapy and nonsteroidal anti-inflammatory drugs

Hypotension and/or renal insufficiency can occur in the setting of volume depletion from severe diarrhea. At the onset of any diarrhea, subjects should be instructed to increase fluid intake to help maintain fluid and electrolyte balance during episodes of diarrhea. Parenteral hydration should be started if oral hydration is not sufficient. The investigator should consider interrupting antihypertensive therapy and nonsteroidal anti-inflammatory drugs, if medically appropriate.

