6.6.1. Premedication to Prevent Hypersensitivity Reaction

Histamine is a major mediator of anaphylactic/anaphylactoid responses in man, such as those induced by Cremophor EL, an excipient in AL101. The premedication regimen below is based on clinical experience with other compounds containing Cremophor EL.

In order to prevent a hypersensitivity reaction, all subjects initiating AL101 treatment will be premedicated approximately 1 hour prior to the infusion of AL101 with the following regimen:

- H1-blocker (for example, diphenhydramine 25 to 50 mg oral or equivalent), and
- H2-blocker (for example, famotidine 20 to 40 mg oral or equivalent).

For subjects who remain on study for more than 4 doses of AL101 without any evidence of infusion-related reaction, modification of the premedication regimen may be considered at the discretion of the investigator, with notification of the Sponsor's Medical Monitor. At this time, 1 of the 2 histamine blockers may be discontinued; if there is still no evidence of infusion-related reaction with the next 2 doses of AL101, the other may be discontinued. If under this discontinuation plan, the subject has an infusion-related reaction resulting in medical treatment, premedication with H1- and/or H2-blockers (as appropriate) should be resumed for subsequent doses.

If a subject experiences a Grade 3 or 4 infusion-related reaction despite pretreatment with the H1- and H2-blockers then the subject, if re-treated, should also be premedicated with corticosteroids (as described in Section 6.6.2) in addition to the H1- and H2-blockers). In the event that a subject has a repeat Grade 3 or 4 infusion-related reaction despite premedication with H1- and H2-blockers and steroid, the subject must not receive any further treatment with AL101, unless agreed by the Sponsor/Medical Monitor and investigator that it is in the subject's best interest to continue treatment (e.g. subject has had a response to therapy) and appropriate safety measures can be implemented. Such measures may include dose reduction, increased infusion time, initial lower infusion rate with gradual increases, and/or premedication with multiple doses of dexamethasone. These measures have been used to allow re-treatment after infusion reactions with other agents, including IXEMPRA and Taxol (Peereboom, 1993).

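### Three AL101 toxicity rules conflict as written: stopping after severe infusion reactions, stopping for diarrhea unresolved at 14 days, and dosing after a first related Grade 3 event at 6 mg QW

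*Combined protocol and SAP*

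**What the plan says.** **Infusion reactions.** The graded list in Section 6.4.1 ends with: "Discontinue the subject from IP for a Grade 4 or for a second episode of a Grade 3 reaction". The closing text of that section says: "Retreatment after a Grade 3 or greater hypersensitivity reaction despite premedication should be discussed between the" sponsor's Medical Monitor and the investigator. Section 6.6.1 begins a premedication instruction with: "If a subject experiences a Grade 3 or 4 infusion-related reaction despite pretreatment with the H1- and H2-blockers then the subject, if re-treated", and adds corticosteroids for that subject. After a repeat Grade 3 or 4 reaction despite full premedication, it says "the subject must not receive any further treatment with AL101, unless agreed by the Sponsor/Medical Monitor and investigator" that continuing is in the subject's best interest and that safety measures can be put in place. Table 3 has a row for Grade 4 non-hematologic events, which stops AL101 permanently. Its row for infusion reactions gives no rule of its own: "For dose modification and management of infusion-related reactions, refer to Section 6.4.1".

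**Diarrhea at 14 days.** The Grade 2 and Grade 3 diarrhea rows of Table 3 state: "If the diarrhea does not resolve to Grade 1 by 14 days, the subject will be discontinued from IP", with a reference to Section 7.2. Item 2 of Section 6.4.2 says the same. Item 3 of Section 6.4.2 says: "If the diarrhea does not resolve to Grade 1 by 14 days, the subject will be temporarily discontinued from IP", and makes the stop permanent only once the interruption exceeds 28 days.

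**First related Grade 3 non-hematologic event at 6 mg QW.** The running text of Section 6.4 prescribes a reduction of one dose level, apart from certain isolated electrolyte abnormalities. In the 6 mg column of Table 3, the rows for Grade 3 diarrhea and for any other related Grade 3 non-hematologic event keep 6 mg and move to two weeks on, one week off. They reduce the dose only from the second episode.

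**The concern.** For each of these events, two sites could act differently and each point to the protocol. The rules decide whether a subject is re-exposed after a severe infusion reaction, whether treatment ends for unresolved diarrhea, and what dose follows a first serious toxicity.

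The events are foreseeable. Section 4.3 reports Grade 3 diarrhea in 8 of 43 subjects in the first-in-human study and in 2 of 34 in the ongoing adenoid cystic carcinoma study. Section 8.3.5.2 reports one Grade 3 anaphylaxis at 4 mg.

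There are analysis consequences, though they are secondary. Who stops AL101 feeds the tabulation in Section 9.3.4 of adverse events that led to discontinuation. Permanent discontinuation also triggers the End of Study visit (Section 7.2). It may lengthen the scan interval from 8 weeks to 3 months for subjects who stop for toxicity (Table 5).

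**Working it through.** No planned figure is at issue, so the check sets the passages side by side, with one dose calculation for the third conflict.

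**1. Infusion reactions**

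| Event | 6.4.1 list | 6.4.1 closing text | 6.6.1 | Table 3 |
|---|---|---|---|---|
| First Grade 3 | No stop | Discuss before re-treatment | Re-treatment foreseen, corticosteroid added | Refers to 6.4.1 |
| Grade 4 | Stop | Discuss before re-treatment | Re-treatment foreseen, corticosteroid added | Refers to 6.4.1; Grade 4 non-hematologic row stops permanently |
| Second Grade 3 | Stop | Discuss before re-treatment | Stop unless agreed otherwise | Refers to 6.4.1 |

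The first row is consistent. The other two are not. The Table 3 cross-reference does not settle the matter, because the unconditional stop and the open discussion are both in Section 6.4.1. Section 6.4.1 also says that its listed grades are not CTCAE grades, while dose modification uses CTCAE v5.0. It is therefore unclear which scale the stop rule uses. This does not remove the conflict, since a reaction that is Grade 4 on both scales falls under both rules.

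**2. Diarrhea at 14 days**

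Take a subject still above Grade 1 at day 14 who then recovers while the interruption is within 28 days. Under Table 3 and item 2 of Section 6.4.2 the subject is off AL101. Under item 3 the subject may resume.

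Reading the Table 3 sentence as temporary fits poorly, for two reasons:
- The same rows have already interrupted AL101 until recovery to Grade 1 or below, so a temporary stop at day 14 would add nothing.
- The sentence uses the same verb and the same Section 7.2 reference as the 28-day stop beside it, and Section 7.2 opens with permanent discontinuation.

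The 14-day limit counts time to resolution and the 28-day limit counts time off treatment. No fixed gap in days between the two rules can be given.

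**3. First related Grade 3 event at 6 mg QW**

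Inputs: the dose levels 6, 4 and 2.4 mg and the schedule change from Table 3; the one-level reduction from the Section 6.4 text. Mean weekly dose = total dose / weeks, over 12 weeks (four 3-week blocks).

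- Table 3, first episode: (6 + 6 + 0) × 4 = 48 mg in 8 infusions; 48 / 12 = 4.0 mg/week.
- Section 6.4 text, one level down: 4 × 12 = 48 mg in 12 infusions; 48 / 12 = 4.0 mg/week.
- Second event, Table 3: 4 mg QW.
- Second event, Section 6.4 text applied again (6 to 4 to 2.4): 2.4 mg QW.
- Difference at the second event: (4 − 2.4) / 4 = 0.40, so 40% lower.

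Equal averages after the first event do not reconcile the rules. Table 3 treats the schedule change and the dose decrease as successive steps, and the dose per infusion differs (6 or 4 mg). The conflict is confined to these two rows in the 6 mg column. The 4 mg column of the same rows, and the AST/ALT and persistent Grade 3 triglyceride rows, agree with the Section 6.4 text.

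**The case against.** **Infusion reactions.** A site that stops AL101 after a Grade 4 or second Grade 3 reaction breaches none of the cited passages. The closing text of Section 6.4.1 adds a discussion before re-treatment and grants no permission. The first Section 6.6.1 sentence is conditional. The default in Section 6.6.1 after a repeat reaction is also to stop. Section 6.4.1 presents its list as recommendations subject to investigator judgment. It stands that stopping is always compliant. But re-treating under the Section 6.6.1 exception breaches the unqualified stop rule in Section 6.4.1, and nothing says which prevails.

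**Diarrhea.** Item 3 joins the 14-day and 28-day limits explicitly and could be read as explaining the shorter wording elsewhere. Section 6.4.2 also defers to clinical judgment. This is a possible reading, but the text does not compel it, and Section 6.4.2 contradicts itself between items 2 and 3.

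**First Grade 3 event.** Section 6.4 opens by pointing to Table 3, and a specific row would normally override general text. The current amendment summary shows that the schedule change was deliberate for diarrhea. That makes the intent likely for the diarrhea row. It does not reach the row for any other Grade 3 event, which is almost as general as the running text and which the summary does not name. The 40% figure needs a reader who applies the running text twice, and it arises only at a second event.

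**Safeguards.** Section 7.2 and the closing text of Section 6.4.1 bring in the Medical Monitor before restart after related serious reactions and severe infusion reactions. Weekly investigator calls and quarterly DMC reviews add oversight. These reduce the risk of inconsistent handling. They do not remove it, because everyone involved works from the same text, and non-serious diarrhea does not pass through the Section 7.2 approval.

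**Conclusion.** The concern holds. There are three conflicts in current operative text:
- Infusion reactions: two event types, any Grade 4 and a second Grade 3.
- Diarrhea: Grade 2 or 3 unresolved at 14 days, at either dose.
- A first related Grade 3 non-hematologic event at 6 mg QW, in two Table 3 rows.

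For the third, exposure averages 4.0 mg/week under both rules after the first event and differs by 40% after a second. That figure assumes the Section 6.4 reduction is applied at each event using the Table 3 dose levels.

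How often these events will occur in this trial, and any effect on ORR, cannot be computed from the documents, and none is claimed. The reason to act is patient safety and uniform conduct, with a smaller benefit to the reporting of discontinuations. It should be corrected, and it does not bear on the sample size or the primary test. This review takes no position on which clinical rule is right.

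**What to change.** Reconcile the passages in a protocol amendment so that each event has one stated consequence, or state which passage takes precedence:

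- **Infusion reactions:** align the stop rule in the Section 6.4.1 list and the Grade 4 non-hematologic row of Table 3 with the closing text of Section 6.4.1 and with Section 6.6.1. As a minor clarification, say which grading scale the stop rule uses.
- **Diarrhea at 14 days:** align the Grade 2 and Grade 3 rows of Table 3 and item 2 of Section 6.4.2 with item 3, and say whether the 14-day stop is temporary or permanent.
- **First related Grade 3 event:** align the Section 6.4 text with the 6 mg QW column of the Grade 3 diarrhea row and the row for any other Grade 3 non-hematologic event.

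The sponsor's clinical team decides which rule stands in each case. The cost is amendment wording, with no added patients, visits or procedures.

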6.4.2. Guidelines for Management of Diarrhea

The guidelines for the management of diarrhea are included in [Table 3](#) and are not meant to replace the clinical judgment of the investigator / treating physician(s) or an institutional diarrhea management protocol which adheres to most current medical standards.

1. Treat with loperamide

Loperamide should be started at the earliest sign of (1) a poorly formed or loose stool, (2) the occurrence of 1 to 2 more bowel movements than usual in 1 day, or (3) an increase in stool volume or liquidity. Loperamide may be taken in the following manners: 4 mg at the first onset of diarrhea, then 2 mg every 2 hours around-the-clock until diarrhea free for at least 12 hours. Subjects may take loperamide 4 mg every 4 hours during the night. This dosing regimen is higher than the standard dose of loperamide, but is typical for the treatment of diarrhea caused by anticancer therapy ([Real, 2009](#)). These doses should not be used for more than 48 hours due to the risk of paralytic ileus. Subjects should be provided with loperamide at the initial treatment visit so that they have sufficient supply on hand in case antidiarrheal support is required. It is important that loperamide is taken as instructed, as some cases of higher-grade diarrhea have occurred in subjects not taking the maximum doses, and these cases have improved after loperamide was taken more frequently. For subjects that cannot tolerate loperamide or do not get adequate relief with maximum doses, standard doses of LOMOTIL® (diphenoxylate/atropine) may be added or used instead of loperamide. Additional antidiarrheal measures, such as octreotide, may be used at the discretion of the investigator or treating physician.

2. Treat with dexamethasone

For Grade 2 or 3 diarrhea that is not adequately controlled with loperamide and dose interruption, administration of corticosteroid may be considered at the discretion of the treating physician/investigator. The subject may be treated with dexamethasone at a dose of 8 mg Q8 hours for up to 5 days. If there still no improvement in symptoms, the subject may continue with the dexamethasone or consider switching to budesonide 9 mg QD. Refer to Section [6.6.2](#) for additional instructions on premedication with steroids.

If the diarrhea does not resolve to Grade 1 by 14 days, the subject will be discontinued from IP. If treatment interruption is longer than 28 days, the subject will be discontinued from IP (refer to Section [7.2](#) for handing IP discontinuation).

For Grade 4 diarrhea, the subject must be discontinued from IP (refer to Section [7.2](#) for handing IP discontinuation).

3. Interrupt AL 101 dosing

For Grade 2 or 3 diarrhea that is not controlled (i.e., to Grade 1) with loperamide, dosing of AL101 should be interrupted, as continued dosing is likely to result in increased severity of diarrhea. In addition, evaluation of infectious causes should be considered. Based on the mechanism of action and preliminary clinical experience, full gastrointestinal (GI) tract recovery will likely take longer than the time for diarrhea to resolve. Thus, interruption for 5 days to 7 days beyond the resolution of diarrhea should be considered. Depending on the severity, time to onset, and time to resolution of diarrhea, reduction of AL101 dose and/or frequency, omission of future doses, or corticosteroid co-administration should be considered (as outlined in Section 6.6.2). If the diarrhea does not resolve to Grade 1 by 14 days, the subject will be temporarily discontinued from IP. If IP interruption is longer than 28 days, the subject will be permanently discontinued from IP (refer to Section 7.2 for handling IP discontinuation).

4. Increase fluid intake and, if applicable, consider stopping antihypertensive therapy and nonsteroidal anti-inflammatory drugs

Hypotension and/or renal insufficiency can occur in the setting of volume depletion from severe diarrhea. At the onset of any diarrhea, subjects should be instructed to increase fluid intake to help maintain fluid and electrolyte balance during episodes of diarrhea. Parenteral hydration should be started if oral hydration is not sufficient. The investigator should consider interrupting antihypertensive therapy and nonsteroidal anti-inflammatory drugs, if medically appropriate.

